Aim 1) to examine if patients randomly assigned to a brief overdose prevention intervention report reduced overdose risk behaviors (e.g., higher dose, concurrent alcohol use, concurrent other drug/medication use, returning to normal dose after breaks in use) over one year of follow-up compared to patients assigned to equal attention EUC.

Aim 2) to examine if patients randomly assigned to a brief overdose prevention intervention have lower total quantities of opioids prescribed (from pharmacy fill records) and aberrant opioid use (e.g., using for reasons other than pain, obtaining opioids from someone other than primary provider) over one year of follow-up compared to patients assigned to equal attention EUC.

The study will include two **secondary aims**: **1)** to examine if patients randomly assigned to the brief intervention have fewer non-fatal overdoses and other medication-related adverse events (emergency department visits, over-sedation, injuries), better functioning, and more often store and dispose of opioids safely compared to patients assigned to EUC; and **2)** to examine mediators (motivation and self-efficacy) and moderators (OIF/OEF/OND status, baseline mental health) of intervention effects.

The proposed POST study will increase our understanding of strategies to reduce adverse outcomes related to prescription opioid use, namely, risk of overdose, among VHA primary care patients. This study is the next logical step in addressing the risks of prescription opioid use among VHA patients, providing critical, initial data to inform VHA clinicians to prevent adverse opioid-related outcomes. Knowledge generated from

this pragmatic trial is likely to have broad implications for improving safe opioid use, the enhancement of PC-MHI services, and the quality of pain care for current and future VHA patients.

BACKGROUND

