services that serve heroin users.³⁰ The sole exception to this is one program that used this model in primary care to provide naloxone to family members of patients who are prescribed OAs.³¹ Extant evidence for these programs is observational. Additionally, although it has been established that overdoses among heroin users are often witnessed,²⁹ it is unknown how often OA overdoses among pain patients occur in the presence of others. A recent cost-effectiveness analysis predicted that, even if 20% of the heroin users in a community were trained in naloxone distribution, only 6% of heroin overdoses would be prevented.³² These data suggest the need for complementary approaches aimed at reducing an individual's overdose risk behavior. Although the recent initiative to provide naloxone to VHA patients recommends that providers complement the naloxone training with patient education, this education has not been tested, and may not be sufficient for altering substance use-related behaviors.

Relevant conceptual models. The intervention will be studied as a selective prevention program, in that participants will be on long-term OA therapy and have a risk indicator for overdose (moderate to high dose). Overdose death, a highly significant but relatively rare outcome, would not be an appropriate primary outcome. Instead the primary outcomes will be overdose risk behavior and OA use (aberrant use or pattern of increasing dose), and secondary outcomes are self-reported non-fatal overdoses, other OA-related adverse events, functioning, and safe OA handling.

Our framework is informed by Ballantyne & Mao's model of adverse effects of OAs. Repeated OA use leads to pharmacological tolerance and increased pain sensitivity, both of which contribute to apparent tolerance, and a need, or perceived need, for a dose increase. We add that OA tolerance and pain sensitivity increase the likelihood of aberrant use, which in turn also leads to dose increases, and subsequent adverse outcomes. The development of tolerance and dose increases can lead to overdose risk behaviors (e.g., consuming a high total dose, breaks in use with resumption of normal use). These processes can be cyclical. Additionally, reducing the proportion of patients on potentially unnecessarily high doses of OAs is a goal of the Opioid Safety Initiative. The proposed intervention may provide a complementary approach by decreasing factors that lead to dose escalations and aberrant use.

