Measures. Data will be collected through a combination of self-report, medical records abstraction, and UDS. In general, the baseline survey will assess past year or lifetime while the follow-up assessments will assess the period since the last assessment. For self-report data, questionnaires with established reliability and validity will be used whenever possible. Reviews suggest that self-report drug use data has a moderate to strong degree of reliability and validity.⁸⁰ The accuracy of self-reported information on substance use is enhanced when confidentiality is ensured and the interview is administered when the respondent is not intoxicated.⁸¹ The voluntary UDS will be used to improve the validity of self-reported substance use.

Measure title	Baseline	Post-Intervention	Follow-ups
Current Opiate Misuse Measure (COMM)	X		X
Overdose Risk Behaviors (ORB)	X		X
Overdose Experiences, Self –Alcohol (OESWA)	X		X
Overdose Experiences, Self and Witnessed – Drugs (OESWD)	X		X
Treatment Service Review (TSR)	X		X
Alternative Therapies (AT)	X		X
Revised Injury Behavior Checklist (RIBC)	X		X
Pain Treatment Satisfaction Scale (PTSS)	X		X
Safe Storage and Disposal of OAs	X		X
Veterans RAND 12-Item Health Survey (VR-12)	X		X
Knowledge of Overdose Risk Factors (OK)	X	X	X
Overdose Education and Naloxone Distribution (OEND)	X		X

Behavioral Intentions (BI)	X	X	X
Self-Efficacy-Overdose Self (SEOS)	X	X	X
Perceived Satisfaction and Utility (PSU – I & PSU – C)		X	
National Comorbidity Survey (NCS)	X		X
Brief Pain Inventory – Short Form (BPI)	X		X
Pain, Enjoyment and General Activity Scale (PEG)	X		X
Centrality of Pain Scale (CPS)	X		X
Addiction Severity Index (ASI)	X		X
Alcohol, Smoking and Substance Involvement Treatment (ASSIST)	X		X
Demographic information	X	X	X
Military service information (MSI) not individually labeled but included in Demographics	X		X

Outcomes. (Measured at Baseline and Follow-up, except where noted)

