Treatment Use (including ED): Use of specific types of clinical services will be assessed with questions adapted from the Treatment Service Review (TSR).⁸⁵ For ED use, participants will be asked “how many times did you visit an emergency room?” and asked what were the problems for which they were seeking treatment and the date of each visit. Parallel questions will assess non-VHA use of addictions, pain, and mental health services. We will assess alternative pain treatment (AT) modalities utilized during baseline and a more extensive list of pain treatments and self-management strategies during follow-up assessments.

Injuries: The Revised Injury Behavior Checklist (RIBC) for adults⁸⁶ will be used to identify 4 types of injuries, including those not resulting in use of ED services (overdose will be excluded from this measure).

Over-sedation: Pain Treatment Satisfaction Scale (PTSS)⁸⁷ is a 12-item tool designed to assess the OA-related side effects on a scale of 0 (“Did not experience” to 5 (“Extremely bothered”). Over-sedation will be measured as “Excessive fatigue”, “inability to concentrate”, and/or “drowsiness.”

Safe Storage and Disposal of OAs: We will adapt items by McCauley and colleagues⁸⁸ designed to assess knowledge of safe storage and disposal of OAs. This measure is sensitive to the effects of a web-based psychoeducation on safe OA storage and disposal.

Functioning: We will use the first item from the Veterans RAND 12-item Healthy Survey (VR-12)⁸⁹. In the interest of reducing patient burden, we will use the single item. This is consistent with health status items

used in many national health studies^{90, 91}.

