Aim 1 analyses. Hypothesis 1: Participants randomized to the intervention condition will report fewer overdose risk behaviors than EUC participants at follow-up. The overdose risk behavior is conceptually a composite count of number of behaviors. However, prior to initiating modeling, we will examine the distribution of responses to individual items on the overdose risk behavior assessment as well as the distribution of the overall composite count. Primary analyses will consist of GLMs to examine group (Intervention vs. EUC) as the primary independent variable at each time point and a GLMM to examine the average effect of the intervention over all assessments. If GLM findings suggest that the impact of the intervention may vary by assessment period, this will be examined using a time by group interaction term.

Aim 2 analyses. Hypothesis 2a: Participants randomized to the intervention condition will have lower average MEM/day doses and MPRs than EUC participants over follow-up. Hypothesis 2b: Participants randomized to the intervention condition will report lower levels of aberrant OA use than EUC participants over follow-up. Aim 2 dependent variables will include both objective measures based on pharmacy data and self-reported aberrant use. Prescribed OA dose will reflect escalating doses (likely due to patient request) and high total doses after combining regularly scheduled and "as needed" OAs.¹² An MPR⁸² greater than 1 identifies potential overuse based whether new fills frequently occur before the days supplied by a prior fill have elapsed. The distribution of the daily dose, MPR, and COMM scores will be examined to select appropriate models. The same analysis strategy used to test intervention effects in GLMs and GLMMs for Aim 1 will be used for the dependent variables in Aim 2.

Secondary aim 1 analyses. Hypothesis 3: Participants randomized to the intervention condition will have fewer non-fatal overdoses, fewer injuries and other OA-related adverse events, and better OA storage and disposal behaviors and better functioning than EUC participants. Analysis will follow the general GLM and GLMM framework used in the Aims 1 and 2 analyses, but a survival analysis approach using Cox proportional hazards regression modeling will also be used to examine time-to-event data (non-fatal overdoses and emergency department visits).

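### Safe storage and disposal is hypothesised as behaviour, but the only instrument described is adapted from knowledge items, so as described the outcome does not test the hypothesis

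*Combined protocol and SAP*

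**What the plan says.** Three places treat this outcome as something patients do. The specific aims, under secondary aim 1, ask whether intervention patients "more often store and dispose of opioids safely compared to patients assigned to EUC". The Background section on conceptual models ends its list of secondary outcomes with "functioning, and safe OA handling". In the analysis plan, Hypothesis 3 (Secondary aim 1 analyses) predicts "better OA storage and disposal behaviors and better functioning than EUC participants".

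The instrument is described differently. Under Secondary Outcomes in the Measures section, the entry opens "We will adapt items by" a cited research group and characterises those items as "designed to assess knowledge of safe storage and disposal of OAs". The support offered is: "This measure is sensitive to the effects of a web-based psychoeducation on safe OA storage and disposal". The measures schedule lists it as "Safe Storage and Disposal of OAs", at baseline and the follow-ups but not at the post-intervention assessment.

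**The concern.** Knowing how opioids should be stored and disposed of is not the same as doing it. If the score reflects knowledge, a difference between arms would show that one arm knows more. It would not show whether tablets are locked away or leftovers discarded safely.

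This matters for interpretation because the intervention session covers the topic directly: it reviews safe storage and disposal in its Guide phase and discusses storage strategies in its Choose phase. A knowledge score could rise because the material was taught, with no change at home. Reported under Hypothesis 3, that result would read as safer behaviour, and the behavioural question would remain open.

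**Working it through.** No arithmetic applies. The plan states no effect size or power specific to storage and disposal, so there is no figure to reproduce. The check sets the relevant sections side by side.

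1. **Construct in the aim, the conceptual model and the hypothesis.** All three use the language of practice: how often patients store and dispose safely, how they handle opioids, and their storage and disposal behaviours.

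2. **Construct in the instrument.** The one content description is knowledge. The evidence offered is responsiveness to an educational programme. Nothing states that the items record what patients do.

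3. **Search for another measure.** The schedule has one storage and disposal entry. The content listed for the overdose risk behaviour measure covers high dose, combining substances, route, using alone, and resuming the usual dose after a break; driving after opioid use is added later in the section. The content listed for the opioid misuse measure covers source, departures from the prescription, and reasons for use. Neither list mentions storage or disposal. The chart and administrative extraction covers prescribing, service use, diagnoses, other medication and mortality, and would not show how tablets are kept at home. Elsewhere, storage and disposal appear only as content of the intervention session.

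4. **The plan's own distinction.** For overdose risk, the protocol separates the two constructs. Behaviours are an outcome with their own instrument, while knowledge of risk factors is listed among mediators and process measures. For storage and disposal, items described as knowledge stand in the outcome position with no companion behaviour measure.

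5. **The plan's own rationale.** The Background argues that behaviour-change methods are likely to achieve more than education alone, and doubts that the education given alongside naloxone is enough to change substance-use behaviour. On that reasoning, knowledge cannot be assumed to stand in for behaviour.

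Steps 1 to 3 establish the mismatch. Steps 4 and 5 show that it matters by the protocol's own standards.

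**The case against.** The strongest reply is that the Measures entry is loosely worded rather than wrong. The items are to be adapted, and the reference to knowledge most naturally describes the source items. The adapted version is not reproduced and might ask about practice. Several features suggest it was meant as a behavioural outcome:

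- its title in the schedule does not call it knowledge, whereas the overdose checklist's title does;
- it is omitted from the post-test, which is where immediate change in knowledge is measured;
- follow-up questions in general cover the time since the previous assessment, a frame that suits practice items;
- it is classed as an outcome and not as a process measure.

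This stands in part. A reader might infer that the measure cannot answer Hypothesis 3 at all; the documents do not support that, because the adapted items are unseen. But none of these features says what the items ask, and the only content statement in the plan is knowledge.

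A reader might also infer a bias in favour of the intervention, since that arm is taught the topic. The documents do not establish this either. Both arms go through the long-term opioid consent and the VHA opioid-safety pamphlet with a therapist, and the protocol expects patients in both arms to gain from safety education. The content ruled out of the control session is tailoring, motivational elements and overdose risk behaviours; storage is not named. Whether the pamphlet covers storage cannot be seen, so the difference in taught content between arms is unknown. Outcomes are also taken at 3, 6 and 12 months, so they are not immediate recall.

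Finally, practice items would not remove every bias: patients counselled on storage may report what they think is wanted. That is a fair limit on the remedy. It does not justify using a different construct.

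**Conclusion.** The mismatch is real. As described, the storage and disposal outcome does not test the behavioural part of Hypothesis 3, and a difference in knowledge could be presented as a difference in behaviour. The conclusion rests on the Measures entry being taken as written and on there being no behaviour item in parts of the survey that the protocol does not describe. If the adapted items already record practice, what remains is a description to correct and a score to define.

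Neither the size nor the direction of any bias can be given. The reach is limited to one component of a secondary hypothesis that also covers non-fatal overdoses, injuries, other adverse events and functioning. The primary aims, their analyses and the sample size are unaffected. It is still worth fixing, because the remedy is specific and cheap.

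**What to change.** At baseline and each follow-up, have the adapted items ask what the participant actually did over the assessment period: where opioids were kept, whether they were locked up, and how any leftovers were disposed of. State in the Measures section how these items are scored, and name that score as the storage and disposal outcome for Hypothesis 3. Keep the knowledge items as a process measure beside the overdose-knowledge checklist.

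If the items are already fixed as knowledge items, reword secondary aim 1 and Hypothesis 3 to refer to knowledge and report the result in those terms.

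The cost is a few survey items on an assessment already scheduled, or the rewording of one aim and one hypothesis; no visits are added. The downside of the first option is that the new items would have less prior validation and would remain self-report, so they are open to socially desirable responding. The report should say so.

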
Mediators and process measures. (*Baseline, Post-Test and Follow-up, except where noted*)

Knowledge of Overdose Risk Factors. Knowledge of overdose risk factors (OK) will be assessed with a checklist adapted from prior studies²⁶ with additional items for OA overdose specifically (OEND). In our pilot RCT, 56% of participants misidentified at least one risk factor. In addition, at Baseline and Follow-up, we will assess participant's involvement in overdose education and naloxone distribution.

Motivation and Self-Efficacy. Behavioral intentions (motivation; BI), self-efficacy, and readiness (SEOS) to change will be measured with 6 visual analog rulers.⁹² These constructs are considered critical to ME interventions.¹⁰

Perceived Satisfaction and Utility (Post-test only). A five-point Likert scale (from "really didn't like it" to "liked it a lot") will elicit satisfaction (PSU-I & C).⁹³ We will use similarly-structured questions⁹⁴ to measure the perceived helpfulness of specific intervention components.

Other factors. (*Baseline and Follow-up, except where noted; collected to inform later implementation, to characterize study sample, and/or to examine moderators of effect*)

Suicidality. We will use select modified items (3) from the National Comorbidity Survey (NCS⁹⁵) that will assess past 12 month suicidal ideation and suicide attempts. Follow-up assessments will inquire about the time since last assessment.

Driving after consuming OAs. For our prior work, we adapted items from the National Survey of Drinking and Driving Attitudes and Behaviors⁹⁶ to OA use (included in ORB). Frequency is assessed with a 5 point Likert scale.

Pain Severity and Functioning. We will use select items (7) from the Brief Pain Inventory-Short Form (BPI)⁹⁷ to assess pain interference on a 11-point numeric rating scale (0=Does not interfere, 10=Completely interferes). The Pain, Enjoyment and General Activity scale (PEG)⁹⁸ is a 3-item questionnaire designed to measure chronic pain in a primary care setting. The Centrality of Pain Scale (CPS)⁹⁹ is a 10-item scale used to assess how patients perceive the role of chronic pain in their lives. The CPS has high internal consistency (Cronbach's alpha = .902).

Alcohol and Drug Use Severity. The Addiction Severity Index (ASI)¹⁰⁰ will be modified to allow participants to self-administer the questionnaire. We will use select items (7) from the ASSIST (WHO¹⁰¹) to assess alcohol use and problems.

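### Functioning in Hypothesis 3 rests on one general-health item, while BPI pain interference and the PEG, collected at the same visits, have no planned between-arm analysis

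*Combined protocol and SAP*

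**What the plan says.** Better functioning is part of the first secondary aim. In the Analysis plan (*Secondary aim 1 analyses*), Hypothesis 3 predicts "better OA storage and disposal behaviors and better functioning than EUC participants". The general GLM and GLMM framework of Aims 1 and 2 applies to it.

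Under *Measures, Secondary Outcomes, Functioning*, the measure is the first VR-12 item alone. The reason given is burden: "In the interest of reducing patient burden, we will use the single item". The next sentence begins "This is consistent with health status items" and refers to items used in national health studies. The wording of the item is not reproduced.

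Under *Measures, Other factors, Pain Severity and Functioning*, seven BPI items are used "to assess pain interference on a 11-point numeric rating scale", and the PEG "is a 3-item questionnaire designed to measure chronic pain in a primary care setting". The measures table gives the VR-12, BPI and PEG the same schedule: baseline and follow-ups. The purpose stated for the *Other factors* block is "collected to inform later implementation, to characterize study sample, and/or to examine moderators of effect".

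No hypothesis or aim-specific analysis names the BPI or the PEG. The moderators in Hypothesis 4b are OIF/OEF/OND status and baseline psychiatric distress.

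**The concern.** Burden explains taking one VR-12 item instead of twelve. It does not bear on the ten BPI and PEG items, which participants complete anyway. Describing the sample and testing baseline moderators need only baseline values. The follow-up BPI and PEG data therefore have no specified analysis beyond a general reference to later implementation.

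The section *Intervention* describes coping tools such as activity pacing, stretching and exercise. How far pain interferes with life is closer to that content than an overall health rating. Hypothesis 2a also predicts lower opioid doses, so readers will ask whether any reduction cost patients function. A null result on one coarse item would answer that poorly. If interference is not pre-specified, a later between-arm comparison of it would be post hoc and open to the charge of selective reporting.

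**Working it through.** **Inputs from the documents.** *Power analysis*: 180 per arm analysed (450 × 0.80 = 360), two-sided α = 0.05, 80% power at a standardized effect of 0.30 for continuous outcomes. The examples given there are opioid dose and aberrant use; functioning is not named.

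**Inputs assumed.** The documents give no reliability, SD or expected effect for the VR-12 item, the BPI or the PEG. Assumed reliability is 0.5 to 0.8 for the single item and 0.85 to 0.95 for the multi-item scale. Both measures are first assumed to carry the same true effect.

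**Step 1: the plan's own figure.** Power ≈ Φ(d√(n/2) − 1.96) = Φ(0.30 × √90 − 1.96) = Φ(0.886) = 81.2%. A two-sample t-test gives 81.0%. The stated 80% reproduces.

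**Step 2: one visit.** Let the multi-item scale show d = 0.30 (power 81.0%). By classical attenuation the single item shows d = 0.30 × √(single-item reliability / multi-item reliability). Power by t-test with 180 per arm:

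| Single-item reliability | Multi-item 0.85 | Multi-item 0.90 | Multi-item 0.95 |
|---|---|---|---|
| 0.5 | 58.6% | 56.2% | 54.0% |
| 0.6 | 66.5% | 64.0% | 61.6% |
| 0.7 | 73.1% | 70.7% | 68.3% |
| 0.8 | 78.6% | 76.3% | 74.0% |

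The smallest loss is 81.0 − 78.6 = 2.4 points and the largest is 81.0 − 54.0 = 27.0 points. With equal reliabilities the ratio is 1 and the loss is zero.

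**Step 3: averaging over visits.** The GLMM estimates the average effect over the 3-, 6- and 12-month follow-ups. With a stable true score and independent errors, the reliability of a three-visit mean is R = 3r/(1 + 2r). Here 0.30 is taken as the error-free effect, so d = 0.30√r at one visit and 0.30√R for the mean. Power uses the normal approximation of Step 1.

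| Reliability r | Power, one visit | R | Power, three-visit mean |
|---|---|---|---|
| 0.50 | 52.1% | 0.750 | 69.3% |
| 0.60 | 59.7% | 0.818 | 73.1% |
| 0.85 | 74.7% | 0.944 | 79.0% |
| 0.90 | 77.0% | 0.964 | 79.8% |

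For single-item reliability 0.5 to 0.6 against multi-item 0.85 to 0.90, the gap is 15.0 points (74.7 − 59.7) to 24.9 points (77.0 − 52.1) at one visit. It falls to 5.9 points (79.0 − 73.1) to 10.5 points (79.8 − 69.3) for the mean. The anchor differs from Step 2, so only the two columns within this table should be compared.

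**Step 4: unequal true effects.** Steps 2 and 3 give both measures the same true effect, which no document supports. If the intervention moved general health more than pain interference, the ordering could reverse.

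**The case against.** The strongest reply is that the plan discloses its choice and does not contradict itself. Functioning in the secondary aim and in Hypothesis 3 is not limited to pain-related functioning. The BPI items are described as pain interference and the PEG as a measure of chronic pain. Replacing the VR-12 item with BPI interference would swap a broad measure for a narrower one. That stands, and it argues for naming interference beside the VR-12 item instead of simply substituting it.

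The burden sentence is also offered only as a reason for shortening the VR-12. It was never meant to explain the role of the BPI or the PEG. That stands too, and it leaves their follow-up data without any planned comparison.

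A reader might infer that the single item definitely costs power, or that the trial is underpowered for functioning. The documents support neither reading. They give no reliabilities for these measures and make no power claim for functioning. The size of any loss is an assumption, the GLMM average reduces it, and its direction is not guaranteed. A reader might also infer that the VR-12 item misses functioning altogether. The protocol's own labels favour the pain-interference items, but the item's wording is not given, so this remains a judgement.

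**Conclusion.** The point holds as a gap in pre-specification. Functioning is tested with one item that the protocol describes in health-status terms. Two scales placed under a functioning heading and collected on the same schedule have no between-arm analysis.

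The possible loss of sensitivity is 2 to 27 points of power at a single visit. That range rests on the assumed reliabilities, an equal true effect on both measures and 180 per arm. It narrows under visit averaging if errors are independent between visits. It is not an established loss.

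The effect is confined to one secondary outcome.

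**What to change.** Under *Secondary Outcomes, Functioning* and *Secondary aim 1 analyses*:

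- Name the mean of the seven BPI interference items as a functioning (pain interference) outcome for Hypothesis 3.
- Analyse it in the same GLM/GLMM framework with its baseline value as a covariate. This must be written in, because the plan currently adjusts only for variables that differ significantly between groups.
- Keep the VR-12 item and label it general health status.
- State which of the two is the main functioning measure.

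Parts of the text suggest that study activities had already begun: the prescriber focus groups are reported as done, and recruitment by flyer is compared with current procedures. The change should therefore be a dated, justified amendment made before any between-arm outcomes are seen.

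The cost is that amendment and one more secondary test. No new data collection or patient burden is involved.
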